Qsymia provides a potential opportunity to develop an effective treatment plan that would be an adjunct to surgical intervention in the super obese patient. Use of Qsymia in addition to a low-calorie dietary prescription pre-operatively would effectively decrease weight prior to surgical intervention, lowering surgical risk to some extent. Additionally, if continued post-operatively, Qsymia as an adjunct to the post-surgical dietary plan would potentially extend the weight loss horizon so that the probability of the typical weight loss plateau at 12-18 months is decreased. The combination of the pre-operative and post-operative weight loss associated with Qsymia use could significantly diminish the need for a second surgical procedure in super obese patients. We have designed a pilot study to examine the use of Qsymia in super obese patients to determine its potential for decreasing the need for a second weight loss surgery.

Primary Objective

The primary objective of the proposed study is to demonstrate the effectiveness of using Qsymia in the superobese (BMI ≥ 50 kg/m²) as an adjunct to surgical therapy.

Secondary Objectives

Secondary objectives of the proposed study include determining tolerability of Qsymia perioperatively, determining changes in resting metabolic rate postoperatively (3 months and 12 months post-surgery), determining the magnitude of preoperative weight loss and determining the magnitude of weight loss at 12, 18, and 24 months post-surgery.

Treatment Plan

Treatment Group

Patients with a BMI ≥ 50 kg/m² that agree to participate in the experimental group will begin their treatment plan with a medical weight loss diet that includes a low-calorie diet and Qsymia at the recommended treatment dose of 7.5/46 mg daily (following initiation of the titration dose for 2 weeks). The low-calorie diet will be individually tailored based on initial resting metabolic rate measurement and co-morbid conditions. Patients will be medically monitored with once monthly medical visits and also have once monthly visits with a dietitian to review the treatment plan. Patients will receive medical weight loss therapy for a minimum of 3 months prior to proceeding to the laparoscopic sleeve gastrectomy. If a patient opts not to proceed to sleeve gastrectomy, they will continue to receive medical therapy for weight reduction including Qsymia and followed for the duration of the study (i.e., for 2 years).

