Patients will discontinue Qsymia the week prior to the scheduled operation. The sleeve gastrectomy will be performed by one of the surgeons at the Weight Management Center ([name], [name], [name]) using standard laparoscopic technique. Post-operatively, all patients will be provided with dietary counseling and a nutrition prescription for a very low calorie, high protein diet: 500-700 calories, protein goal of 1-1.2g/kg IBW, and 60-75g carbohydrate. Qsymia will be resumed in the second post-operative week at the initial titration dose and increased to the recommended treatment dose of 7.5/46 mg daily. Patients will have standard post-operative surgical follow up at months 1, 3, 6, 9, 12, 18, and 24. During the post-operative phase, all patients will be enrolled in the bariatric support group program that meets on a monthly basis. Patients will also have at least 3 visits with a clinic dietitian to review and update dietary prescriptions. At any point during this course of follow up, a determination can be made that the primary outcome event has occurred if the patient has a weight plateau—defined as weight gain or < 3 lbs weight loss—for 3 consecutive months, remains above a BMI of 39.9 kg/m² and continues to have associated co-morbidities. These patients will be evaluated for the possibility of moving forward to the next operative stage (laparoscopic Roux-en-Y gastric bypass) while all other patients will continue on with medication and diet/exercise therapy.

Control Group

Control subjects for the proposed study will be identified from the patient population at the Wake Forest Baptist Health Weight Management Center. They will be matched to subjects in the treatment group on age, sex, ethnicity, and BMI. They will be a historical control group who had surgery prior to the commencement of the proposed study (retrospective review).

Trial Design

Prospective independent historical case control

Inclusion Criteria

Inclusion criteria for the proposed study are:

- BMI \geq 50 kg/m²
- Determined to be a good candidate for surgery based on medical and psychological exam.
- Willing to participate in a 3-6 month medically supervised weight loss plan prior to surgery.
- Planning to remain in the reasonable vicinity of the Wake Forest Baptist Health Weight Management Center for the duration of the study.

Exclusion Criteria

- History of prior weight loss surgery (removal/conversion from band to sleeve will not be excluded)

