We hypothesize that the study group treated with Qsymia plus surgery will have greater percent weight loss at all time points compared to the group treated with surgery only. We also hypothesize that the study group treated with Qsymia plus surgery will have a higher resting metabolic rate after adjustment for lean body mass compared to the group treated with surgery only.

Other measures obtained by chart review

Height will be measured at all new patient visits and will be repeated at 24 months to account for any changes over the course of participation. Weight is measured at every clinic visit and will be captured for the study at the time points in the table below. Waist circumference will be measured at the level of the umbilicus at the time points reported in the table. Resting metabolic rate will be measured using expired gas analysis via the MEDGem analyzer. This will be measured following the protocol suggested by the manufacturer, including after refraining from eating, drinking, caffeine or exercise for at least 4 hours prior and immediately following a 10 minute period of quiet rest. Body fat percentage will be measured using Bioelectrical Impedance Analysis via the RJL Systems Quantum II. The Quantum II provides body fat percentage as well as a calculation of total lean mass and total fat mass.

Blood Measures

Blood will be drawn at baseline, 3 months, 6 months, 12 months, 18 months and 24 months and stored for use in later analysis.

Boxes marked with UC are tests that are done as part of usual care. Boxes marked with R are tests done for research only.

Test	BL	1m	3m	6m	9m	12m	18m	24m
Resting Metabolic Rate (MEDGem Analyzer)	UC			R		R		R
Body Fat % by Bioelectrical Impedance Analysis (RJL Systems)	UC			R		R		R
Height	UC							R
Weight	UC	UC	UC	UC	UC	UC	UC	UC
Waist Circumference	UC			R		R		R
Blood draw	R		R	R		R	R	R

Monitoring of Side Effects to study medication

Monitoring for side effects will be performed at each visit. Report of suicidal ideation will lead to study discontinuation and withdrawal from medication. Endpoint will be considered reached in this instance.

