The secondary outcomes for this study include percent weight loss and changes in percent body fat and resting metabolic rate. The time points of interest include pre-surgery period (baseline to surgery), baseline to 6 months (post-operative), baseline to 12 months, and baseline to 24 months. Independent T-test statistic will be used to test for differences in the changes scores between the groups at each time point for these continuous variables. Given this pilot study design and exploratory nature of this secondary aim, we will not use the conservative approach of Bonferroni adjustment for multiple comparisons. Therefore, alpha will remain at 0.05 for this family of hypotheses.

Sample size justification/statistical power

We are planning a study with 25 experimental subjects and 20 control subjects. Prior data indicate that the approximate failure rate among controls is 0.7 (Alexandrou et al, 2012). If the true failure rate for experimental subjects is 0.25, we will be able to reject the null hypothesis that the failure rates for experimental and control subjects are equal with probability (power) .840. The Type I error probability associated with this test of this null hypothesis is 0.05. We will use an uncorrected chi-squared statistic to evaluate this null hypothesis.

References

Nguyen, N et al. A review of unmet needs in obesity management. *Obes Surg.* 2012 Jun;22(6):956-66

Alexandrou et al. What is the Actual Fate of Super-Morbid-Obese Patients Who Undergo Laparoscopic Sleeve Gastrectomy as the First Step of a Two-Stage Weight-Reduction Operative Strategy? *Obes Surg* (2012) 22:1623–1628

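### The schedule implies that historical control charts do not routinely hold the post-operative resting metabolic rate and body fat values needed for 6 of the 12 planned secondary tests, and the stated t-test does not carry the lean-mass adjustment in the hypothesis

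*Combined protocol and SAP*

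**What the plan says.** The Control Group section describes the comparison patients: "They will be a historical control group who had surgery prior to the commencement of the proposed study (retrospective review". They are still to be identified, by matching to treated patients on age, sex, ethnicity and BMI.

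The secondary outcomes in the Statistical analysis section are percent weight loss, change in percent body fat and change in RMR. The time points are baseline to surgery, and baseline to 6, 12 and 24 months. On the method it says: "Independent T-test statistic will be used to test for differences in the changes scores between the groups at each time point". The aim is called exploratory and alpha stays at 0.05 per test.

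The hypotheses that follow the Secondary endpoints heading predict for the Qsymia group a "higher resting metabolic rate after adjustment for lean body mass compared to the group treated with surgery only".

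The measurements are described under the heading "Other measures obtained by chart review". That section says of the bioimpedance device: "The Quantum II provides body fat percentage as well as a calculation of total lean mass and total fat mass". The key to the schedule table, printed under Blood Measures, reads: "Boxes marked with UC are tests that are done as part of usual care. Boxes marked with R are tests done for research only".

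**The concern.** A test done only for research would not be expected in the chart of a patient operated on before the research began. On the schedule's own labels, RMR and body fat after baseline are such tests, yet the plan compares their change between the treated patients and those historical controls.

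If the values are missing, the affected tests and the RMR hypothesis cannot be carried out as written. If only some controls have values, those patients may be a selected subset, and the comparison would rest on them without the plan requiring anyone to say so. The plan gives no other source for control values, no check that the charts hold them, and no missing-data approach for these outcomes.

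A second mismatch does not depend on what the charts contain. The RMR hypothesis is conditional on lean body mass, but the stated analysis is a t-test on change scores with no adjustment named. The plan also expects greater weight loss with Qsymia, so adjusted and unadjusted comparisons could give different answers.

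**Working it through.** No figure in the plan bears on this point. Its one computed figure, the power of .840, concerns the primary endpoint and is not used here. The check is a count from the schedule, followed by the precision that would remain.

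**1. Schedule cells at the post-operative time points**

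| Measure | Baseline | 6 m | 12 m | 24 m |
|---|---|---|---|---|
| RMR | UC | R | R | R |
| Body fat % (also gives lean mass) | UC | R | R | R |
| Weight | UC | UC | UC | UC |

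RMR and body fat are blank at 1, 3, 9 and 18 months. For these two measures, usual-care cells at 6, 12 and 24 months number 0 of 6. For weight they number 3 of 3, and the text agrees: "Weight is measured at every clinic visit and will be captured for the study at the time points in the table below".

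**2. Tests affected**

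- Planned secondary tests, read literally: 3 outcomes x 4 time points = 12.
- Post-operative tests of RMR and body fat: 2 outcomes x 3 time points = 6.
- Affected: 6 of 12.

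Lean mass comes from the same bioimpedance test as body fat, so it has the same labels. Each lean-mass-adjusted RMR comparison therefore needs two post-operative values per control, both marked research only.

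**3. Does the time origin matter?** The table does not say whether its months run from enrolment or from surgery. The count of 6 does not depend on this, because every post-baseline RMR and body fat cell is R or blank.

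The origin does matter for the two baseline-to-surgery tests of RMR and body fat. The baseline RMR is taken when the diet is set, since the diet is "individually tailored based on initial resting metabolic rate measurement", and at least 3 months of medical therapy then precede surgery. If months run from surgery, the next value is 6 months post-operative and none is scheduled at surgery. If they run from enrolment, the 6-month column could fall near surgery, because the Inclusion Criteria give a 3-6 month pre-operative plan. The analysis text, which calls its 6-month point post-operative, and the similar surgical follow-up months favour surgery as the origin but do not settle it.

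**4. If only some controls have values.** The share is not in the documents, so the rows below are assumptions. The entries are the between-group difference in change, in SD units, detectable with 80% power at two-sided 0.05 (noncentral t). As a rough check, d = (1.96 + 0.84) x sqrt(1/nT + 1/nC); for 25 and 20 this is 2.80 x sqrt(0.04 + 0.05) = 0.84, against 0.86 from the noncentral t. The plan gives both 20 cases and 25 experimental subjects, so both are shown.

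| Controls with values (of 20) | 25 treated | 20 treated |
|---|---|---|
| 20 | 0.86 | 0.91 |
| 15 | 0.94 | 0.99 |
| 10 | 1.08 | 1.12 |
| 5 | 1.42 | 1.46 |
| 2 | 2.14 | 2.18 |
| 0 | not computable | not computable |

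**5. Precision of the within-group alternative.** The 95% CI half-width for mean change is t(0.975, n-1)/sqrt(n) SDs of change. For n = 20: 2.093/4.472 = 0.47. For n = 25: 2.064/5 = 0.41.

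**The case against.** The strongest reply is that nobody has looked at the charts. The UC/R key is in the present tense and labels this study's tests, no section states what earlier patients at the centre received, and the section heading says chart review. This stands as a limit on strength: the documents show an unverified data source. It does not remove the point, because the table printed after that heading labels these same cells research only.

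A reader might infer that the control values do not exist and that the comparison is impossible. The documents do not go that far, since some earlier charts may hold incidental values.

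A reader might also count eight affected tests by adding the two baseline-to-surgery ones. That depends on the unstated time origin. The wording may also be loose, because the Secondary endpoints section attaches the period before surgery only to weight loss.

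On the adjustment, a reader might infer that a t-test can never answer the RMR hypothesis. That is too strong: a t-test on RMR indexed to lean mass would be one form of adjustment. What stands is that no adjustment is specified. The adjusted models in the Statistical analysis section are stated for the primary endpoint only.

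Finally, this is a pilot and the aim is exploratory. That limits the impact, but exploratory status does not make a test computable without data.

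**Conclusion.** The point holds as an inference from the plan's own schedule. Six of the 12 planned secondary tests, and the lean-mass-adjusted RMR hypothesis, rest on control values that the schedule does not mark as routine. This assumes that UC and R also describe care at the centre before the study began. The missing adjustment in the stated RMR test holds without that assumption.

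The impact is confined to exploratory secondary outcomes. The primary endpoint, post-operative percent weight loss and the baseline comparison of RMR and body composition are not affected. The RMR item under Secondary Objectives asks only for change after surgery and needs no control group. The point should be fixed before analysis; it does not threaten the main conclusion.

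**What to change.** Before any comparison is run, check the charts of the candidate control pool for post-operative RMR and body-composition values. The pool has to be used because the matched set does not yet exist. Fix the minimum number of controls with values in advance; the detectable differences tabulated above are one basis for choosing it.

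- **If values are absent or sparse:** limit between-group secondary tests to percent weight loss, withdraw the between-group RMR hypothesis, and report RMR and body fat as within-group change in Qsymia patients at 6, 12 and 24 months with 95% CIs.
- **If values are adequate:** keep the comparison, report the number of controls with data at each time point, and compare RMR in a model that includes lean mass, which the Quantum II already gives.

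In either case:

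- State whether the schedule's months count from enrolment or from surgery. If from surgery, limit the baseline-to-surgery comparison to weight.
- Reconcile the 3-month RMR time point under Secondary Objectives with the schedule, which has RMR at 6, 12 and 24 months and none at 3.

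The cost is a chart check, which may cover more than 20 charts because it samples the pool, plus changes of wording. No extra tests on participants are needed. The downside is that the between-group claim on RMR and body fat may be lost, and within-group change cannot separate the effect of Qsymia from that of surgery.

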This is an independent case-control study. Analyses will include completers only. Completers are defined as individuals who enter treatment and continue it (Qsymia and/or gastric sleeve) for at least 24 months without reversal or discontinuation. Participants will be recruited until the sample size of 20 cases is obtained. If a participant consents but does not have surgery, this person will not be counted as a case and thus, recruitment will continue.

Data will be entered into and stored in a REDCap database with access given only to individuals who are part of the study team. Study data uploaded will include information from the weekly clinic questionnaire, adverse events, as well as study outcomes (weight at clinic visits), demographic information, etc.

[figure not shown]
Most of the statistical analyses will be conducted using SPSS or SAS. Prior to testing the specific aims, descriptive statistics will be used to characterize the sample. Next, the groups will be compared using the chi-square statistic and T-test statistic to determine whether differences existed between the groups on key variables that may have an effect on outcomes. The case-control matching procedure should insure balance between the treatment groups on sex, age, BMI and ethnicity, but additional analyses will be used to examine the comparability between groups on baseline body composition, waist circumference, and resting metabolic rate.

The primary endpoint for this study is the proportion of patients that meet the criteria to move forward with the second surgical procedure (Roux en Y Gastric Bypass) at any point during follow up. The proportion of the Qsymia treated group that achieves the primary endpoint will be compared to the surgery only group after 24 months of follow up. Unadjusted and adjusted models will be developed to test for differences in the rate of the primary endpoint occurrence by treatment group.

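### Secondary outcomes are compared by unadjusted t-tests on change scores, which use no baseline covariate or matching factor and cannot test the protocol's own lean-mass-adjusted RMR hypothesis

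*Combined protocol and SAP*

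**What the plan says.** The Statistical analysis section lists the outcomes: "The secondary outcomes for this study include percent weight loss and changes in percent body fat and resting metabolic rate". The periods are baseline to surgery and baseline to 6, 12 and 24 months. The method is: "Independent T-test statistic will be used to test for differences in the changes scores between the groups at each time point". No covariate is named. The aim is called exploratory, within a pilot, and there is no multiplicity adjustment: "Therefore, alpha will remain at 0.05 for this family of hypotheses".

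Four other places bear on this:

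- The same section plans both unadjusted and adjusted models, but for the primary endpoint only, and it names no covariates.
- Under Control Group, the controls are historical patients found by retrospective review and matched on age, sex, ethnicity and BMI. Body fat and RMR are not matching factors. For these the Statistical analysis section says that "additional analyses will be used to examine the comparability between groups on baseline body composition, waist circumference, and resting metabolic rate", and it states no consequence if they differ.
- Under Secondary endpoints, the RMR hypothesis is that treated patients will have the higher RMR once lean mass is allowed for.
- In the test schedule, RMR and body fat are usual care at baseline but research-only at 6, 12 and 24 months. Weight is usual care at every visit.

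**The concern.** A t-test on change leaves two kinds of information unused: the relation between baseline and follow-up, and the factors on which the controls were chosen. In a comparison of 40 to 45 patients the lost precision can matter. The groups are not randomised, so baseline differences in the unmatched measures are possible, and the planned comparability check leads to no stated action.

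There is also a plain mismatch between hypothesis and test. A two-sample t-test on change in RMR has no place for lean mass, so it cannot answer the RMR question that the protocol poses.

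**Working it through.** **1. Inputs.** The plan gives no SD, effect size, correlation or power for the secondary outcomes, so there is no figure on this point to reproduce. Its one power figure, 0.840 for the primary endpoint, matters here only through group size. The sample size section says "We are planning a study with 25 experimental subjects and 20 control subjects", while the Statistical analysis section says "Participants will be recruited until the sample size of 20 cases is obtained". With failure rates 0.7 and 0.25, the two-sided uncorrected chi-squared formula gives 0.880 at 25 treated and 20 controls, and 0.8405 at 20 and 20. Both sizes are therefore carried below. Assumptions: baseline-to-follow-up correlation r of 0.4 to 0.8, equal variances, two-sided alpha 0.05, results in baseline SDs.

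**2. Precision, body fat and RMR.** The SD of a change score is sqrt(2(1 − r)). The residual SD after baseline adjustment is sqrt(1 − r²). With balanced baselines the standard error ratio is sqrt((1 + r)/2).

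- r = 0.4: sqrt(0.70) = 0.84; equivalent sample size gain 2/1.4 = 1.43
- r = 0.8: sqrt(0.90) = 0.95; equivalent sample size gain 2/1.8 = 1.11

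Difference detectable with 80% power (noncentral t), t-test then adjusted model:

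| r | 25 treated, 20 controls | 20 and 20 |
|---|---|---|
| 0.5 | 0.860 → 0.745 | 0.909 → 0.788 |
| 0.7 | 0.666 → 0.614 | 0.704 → 0.650 |
| 0.8 | 0.544 → 0.516 | 0.575 → 0.546 |

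**3. Precision, percent weight loss.** This outcome already divides by baseline weight, and BMI is matched, so step 2 does not carry over. If percent loss correlates 0.1 to 0.3 with baseline (assumed), adjustment removes 0.1² to 0.3², that is 1% to 9%, of the variance.

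**4. Chance imbalance.** Given a baseline imbalance d that is chance or measurement noise, the change-score difference is off by −(1 − r)d. For d = 0.5 SD the size is 0.5 × 0.6 = 0.30 SD at r = 0.4 and 0.5 × 0.2 = 0.10 SD at r = 0.8.

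The comparability check could easily miss such an imbalance. The standard error of a baseline difference is sqrt(1/20 + 1/25) = 0.30 SD, so d = 0.5 gives t = 0.5/0.30 = 1.67, p about 0.10. At 20 and 20 the standard error is 0.316 and p is about 0.12.

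**5. Stable difference.** If the groups differ by d as populations and change in parallel, the roles reverse: the change score is unbiased and the adjusted model is off by +(1 − r)d. Simulation with no true effect, d = 0.3 SD, 25 treated and 20 controls, 4,000 runs:

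| Source of imbalance | r | Mean error, change score | Mean error, adjusted | Type I error, adjusted |
|---|---|---|---|---|
| Chance | 0.5 | −0.152 | −0.003 | 4.9% |
| Chance | 0.7 | −0.092 | −0.002 | 4.7% |
| Chance | 0.9 | −0.026 | +0.003 | 5.2% |
| Stable | 0.5 | −0.003 | +0.150 | 9.0% |
| Stable | 0.7 | −0.005 | +0.085 | 7.1% |
| Stable | 0.9 | +0.003 | +0.033 | 5.9% |

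**6. Precision when baselines are unbalanced.** The gain in step 2 and the bias in step 4 do not hold in full together. With d = 0.5 SD at 25 and 20, the variance of the adjusted estimate rises by 0.25/(43 × 0.09) = 6.5%. At r = 0.8 the sample size gain falls from 1.11 to 1.11/1.065 = 1.04.

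**The case against.** An unadjusted change-score t-test is a recognised analysis, and choosing between it and a baseline-adjusted model is a choice between assumptions. With historical controls a stable group difference is at least as plausible as a chance one. In that case the planned test is the sound one and the adjusted model misleads (step 5). This stands, and it is why the change-score result should not be reduced to a descriptive footnote.

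Follow-up RMR and body fat are research-only in the schedule, so patients operated on before the study may lack them. Without those values neither method can be run for the two outcomes that would gain most. This also stands, and it is a larger threat to those comparisons than the choice of model. Percent weight loss, for which control follow-up is usual care, gains little.

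A reader might infer that the planned t-tests are biased by regression to the mean because the groups are not randomised, and that a baseline covariate would cure it. The documents do not support this, because nothing in them shows whether any imbalance would be chance or stable. Nor do they say that imbalance is expected; they say only that comparability will be examined.

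The objection does not reach the RMR hypothesis. The protocol itself calls for adjustment for lean mass, and the planned test provides none.

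**Conclusion.** The point holds as one of efficiency and of fit between hypothesis and test, not as a demonstrated bias. For body fat and RMR the adjusted model's standard error is 0.84 to 0.95 of the t-test's, given r of 0.4 to 0.8, equal variances and near-balanced baselines; none of these can be checked from the documents. For percent weight loss the gain is small. A 0.5 SD imbalance can mislead by 0.10 to 0.30 SD, through the change score if it is chance and through the adjusted model if it is stable, so neither method is guaranteed. The mismatch over lean mass needs no assumption.

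The outcomes are secondary and exploratory, and the primary comparison is unaffected. This is a minor to moderate recommendation.

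**What to change.** - At each time point, pre-specify a linear model of the outcome on group, the baseline value of that measure (baseline BMI for percent weight loss), age and sex. Add ethnicity if numbers allow.
- For RMR, add lean body mass, which the bioimpedance device already supplies, and state at which visit it is taken.
- Report the adjusted difference with its 95% CI. Keep the unadjusted change-score comparison as a named sensitivity analysis and state whether the two agree.
- Apply this to RMR and body fat only where controls have follow-up values, and report how many do.

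The cost is SAP wording and a few degrees of freedom: with 45 patients, from 43 for the t-test to 40 with baseline, age and sex, and 39 with lean mass. No measurement beyond those the t-tests need is called for, apart from lean mass from the same device. The SAP should also state the main limitation: the adjusted estimate assumes that baseline differences are not stable group differences.

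### Controls come from existing charts, yet the plan uses no more of them than treated patients; a 2:1 ratio would add precision without enrolling anyone

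*Combined protocol and SAP*

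**What the plan says.** - **Group sizes.** Sample size justification/statistical power: "We are planning a study with 25 experimental subjects and 20 control subjects". The Statistical analysis section gives a different treated number: "Participants will be recruited until the sample size of 20 cases is obtained".
- **Source of controls.** Control Group: "They will be a historical control group who had surgery prior to the commencement of the proposed study (retrospective review".
- **Matching.** Control Group: "They will be matched to subjects in the treatment group on age, sex, ethnicity, and BMI". No matching ratio or matching tolerance is stated, and nothing is said about whether a control may be used more than once.
- **Power statement.** "Prior data indicate that the approximate failure rate among controls is 0.7"; "If the true failure rate for experimental subjects is 0.25", the null hypothesis is rejected as "equal with probability (power) .840". The test is an uncorrected chi-squared. On alpha: "The Type I error probability associated with this test of this null hypothesis is 0.05". Sidedness is not stated.

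The documents do not explain the choice of 20 controls and do not say how many eligible charts the centre holds.

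**The concern.** The two groups differ greatly in cost. A treated patient needs study drug, at least three months of monthly visits before surgery, and 24 months of follow-up after it. A control needs a chart to be found and abstracted. When one arm is expensive and small and the other comes from records, the usual course is to take more than one control per treated patient. This plan has 0.8 controls per treated patient (25 v 20) or 1.0 (20 v 20).

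What is at stake is the precision of the primary comparison and its tolerance of optimistic assumptions. The power claim rests on a 45-point difference and on a control rate that the plan itself calls approximate. The analysis is also restricted to completers, with no allowance for dropout. Extra controls would give some protection on each count without adding a participant.

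**Working it through.** **Inputs.** Failure rates p_t = 0.25 (treated) and p_c = 0.70 (control), alpha 0.05 and an uncorrected chi-squared test, all from the sample size section. Two-sided testing is my assumption. Treated n is 25 (sample size section) or 20 (Statistical analysis section). Planned controls: 20.

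**Formulas.**
- SE1 = sqrt[p_t(1−p_t)/n_t + p_c(1−p_c)/n_c]
- SE0 = sqrt[p̄(1−p̄)(1/n_t + 1/n_c)], with p̄ the pooled rate
- Power = Φ[(|p_c − p_t| − 1.96·SE0)/SE1]
- 95% half-width = 1.96·SE1

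**Step 1: the plan's own figure.**
- At 25 v 20: p̄ = (25×0.25 + 20×0.70)/45 = 0.45, SE0 = 0.1492, SE1 = 0.1342. Power = Φ[(0.45 − 1.96×0.1492)/0.1342] = Φ(1.17) = 0.880, not .840. Variants at the same sizes do not give .840 either: exact 0.874, continuity-corrected 0.799, unpooled 0.918, one-sided 0.936.
- At 20 v 20: p̄ = 0.475, SE0 = 0.1579, SE1 = 0.1410. Power = Φ(0.997) = 0.8405. The stated figure is therefore the power for 20 v 20, which agrees with the 20 cases in the Statistical analysis section.

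**Step 2: where the variance comes from.**
- 20 v 20: treated 0.1875/20 = 0.009375; control 0.21/20 = 0.0105. Control share = 0.0105/0.019875 = 53%.
- 25 v 20: treated 0.1875/25 = 0.0075; control 0.0105. Control share = 0.0105/0.0180 = 58%.

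**Step 3: more controls at the plan's rates.**

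| Treated | Controls | Power | SE1 | 95% half-width (points) |
|---|---|---|---|---|
| 20 | 20 | 0.840 | 0.141 | 27.6 |
| 20 | 40 | 0.935 | 0.121 | 23.7 |
| 20 | 60 | 0.962 | 0.113 | 22.2 |
| 25 | 20 | 0.880 | 0.134 | 26.3 |
| 25 | 50 | 0.975 | 0.108 | 21.2 |
| 25 | 75 | 0.987 | 0.101 | 19.9 |

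Going to 2:1 narrows the half-width by 27.6 − 23.7 = 3.9 points (20 treated) or 26.3 − 21.2 = 5.1 points (25 treated). Exact enumeration with 20 treated gives power 0.823, 0.936 and 0.958 for 20, 40 and 60 controls, the same pattern.

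**Step 4: a less favourable control rate.** If the control rate were 0.60 (an assumption) and the treated rate stayed at 0.25:
- 20 treated: power 0.62 with 20 controls, 0.75 with 40, 0.80 with 60.
- 25 treated: power 0.67 with 20 controls, 0.84 with 50.

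These powers are for an unmatched two-sample test, the one the plan specifies. A matched-set analysis would give somewhat different values, depending on the within-set correlation, for which the documents give no figure.

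**The case against.** The strongest counter-argument is that the benefit is modest and its price unknown. The study is a pilot, and under its own assumptions it already has power of 0.84 to 0.88. A usable control needs a BMI of at least 50, an earlier sleeve gastrectomy, a match on four factors, and a record good enough to establish a three-month weight plateau and continuing co-morbidity over 24 months. The centre may not have 40 to 75 such charts, and second and third matches may be looser. The third control adds under 3 points of power at the plan's rates (0.935 to 0.962 with 20 treated).

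Much of this stands. It makes the ratio conditional on the pool and shows that most of the gain comes at 2:1. It does not justify stopping at 20 without a count of the eligible charts. Pilot status is a weak defence where the plan makes a formal power claim.

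Two further limits also stand. More controls reduce random error only; they do nothing about bias from historical controls or from the completers-only analysis. They also help less for body fat and resting metabolic rate, whose follow-up tests are marked research-only in the schedule of measures and so may be missing from historical charts.

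A reader might infer that 25 v 20 leaves five treated patients without a match. The documents do not support this. It requires one-to-one matching without reuse of controls, which is nowhere stated; the text is equally compatible with group-level matching, and at 20 v 20 nobody would be unmatched.

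**Conclusion.** The concern holds as a point of efficiency. Neither treated number gives more controls than treated patients, although controls are drawn from records and contribute slightly more than half of the random error in the primary comparison. The gain from 2:1 is similar for both treated numbers, about 9 to 10 points of power at the plan's rates, and larger if the control rate is below 0.70. The plan's test remains valid as it is, and nothing here suggests otherwise.

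The conclusion rests on two-sided alpha of 0.05, on the plan's rates (or the assumed 0.60), on an unmatched test for the power figures, and on a sufficient number of eligible charts. That number is the main unknown. Separately, the sample size statement is inconsistent within the document: the stated power fits 20 v 20, while the sentence containing it plans 25 v 20.

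**What to change.** - **Sample size section.** Replace the fixed number of 20 controls with: *at least 2, and up to 3, historical controls per treated patient, as many as the pool of eligible charts allows within the stated matching limits*. Count the eligible charts before fixing the ratio.
- **Control Group section.** Add the same ratio and state the matching limits; this section currently gives neither.
- **Primary analysis.** Allow for the matched sets.
- **Power statement.** Reconcile the treated number (20 or 25), state whether the test is one- or two-sided, and restate power for the final sizes.

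**Cost.** With 20 treated, 40 − 20 = 20 to 60 − 20 = 40 more charts; with 25 treated, 50 − 20 = 30 to 75 − 20 = 55 more. Charts screened and rejected come on top. Second and third matches may be slightly looser, so balance on the matching factors should be reported. No patient is enrolled and no procedure is added.
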